2.1 Sample size calculation

Sample size: The sample size is based on the primary endpoint of proximal fractional sodium excretion (FE_{Na}), which will be measured using fractional excretion of lithium as a surrogate for proximal sodium handling. Based on preclinical studies, and assuming a baseline FE_{Na} of 22±7, to be able to detect a 40% increase in FE_{Na} with an 80% power and a two-tailed alpha = 0.05, 18 patients per group are required, for a total sample size of n=36. This sample size is similar to those successfully used in previous studies², and sufficient to measure secondary endpoints related to Na⁺ handling^{27,28}, renal function², arterial stiffness, plasma volume⁷, systemic vascular resistance ²⁹ and measures of neurohormonal function^{10,17,18}. Randomization will be stratified to assure equal numbers of HFrEF and HFpEF patients in the ertugliflozin and placebo-treated groups. We anticipate an approximate 50%/50% split in the proportion of participants with HFrEF vs. HFpEF, which will be assessed based on the 2D echo at the time of the baseline physiological testing.

Data Analysis: **The primary outcome** is the difference in proximal sodium reabsorption FE_{Na} (measured using FE_{Li}) with ertugliflozin vs. placebo. **Secondary outcomes** will consist of *within* and *between group* changes in hemodynamic and tubular function parameters and vasoactive mediators in response to combination vs. monotherapy regimens. *Within group* comparisons will be analyzed using repeated measures ANOVA. As in previous work, *between group* comparisons will also be made using a 2-way ANOVA with treatment allocation as the dependent variable. *Post-hoc* analyses will be used to compare means, corrected for multiple comparisons. In pre-specified, exploratory sensitivity analyses, the same endpoints will be examined only in those patients who did not have changes in RAAS inhibitors and/or diuretic agents during the treatment period.

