6.5 Replacement of individual subjects after withdrawal

Patients that meet inclusion criteria will be invited for participation in the study. When patient agrees to participate in the study, informed consent is signed. When patient decides to withdraw after start of the treatment period, new patients can be admitted to the study to reach the required sample size.

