- 3.1. We will assess whether ertugliflozin causes acute and chronic changes in measures of system volume compared to placebo.
- 3.2. We will assess whether ertugliflozin causes acute and chronic changes in measures of systemic water and fluid balance compared to placebo.
- 3.3. We will assess the acute and chronic change of all blood and urine biomarker levels with ertugliflozin compared to placebo.
- 3.4. We will determine whether changes in neurohormones are associated with changes in renal function. To this end, we will determine the association between acute and chronic changes in absolute measures of renal function and the acute and chronic changes in neurohormones with ertugliflozin compared to placebo.

- 3.5. We will determine whether changes in neuro-hemodynamic markers associated with HF patients are associated with changes in arterial stiffness. To this end, we will determine the association between acute and chronic changes in arterial stiffness and the corresponding acute and chronic changes in neuro-hemodynamic markers with ertugliflozin compared to placebo.
- 3.6. We will determine whether changes in neurohormones that are activated in HF patients are associated with changes in blood pressure. To this end, we will determine the association between acute and chronic changes in blood pressure and the acute chronic changes in neurohormones with ertugliflozin compared to placebo.
- 3.7. We will assess the acute and chronic effects of ertugliflozin on the level of oxidative stress markers compared to placebo.
- 3.8. We will assess the acute and chronic changes with ertugliflozin on urine and plasma chemistry marker levels and metabolic parameters compared to placebo.

Outcomes

1. Outcomes for the primary objective:

- 1.1. The primary outcome is measured by the acute and chronic change in lithium clearance from baseline with ertugliflozin vs placebo. $FE(Li^+) = 100 X ([(urine Li^+) X (creatinine plasma)]/[(plasma Li^+) X (creatinine urine)]$
- 1.2. We will also measure the primary objective on these secondary outcomes:a. *Total overall (proximal and distal) tubular sodium handling*
 - $FE(Na^+) = 100 X ([(urine Na^+) X (creatinine plasma)]/[(plasma Na^+) X (creatinine urine)]$ b. Distal sodium handling: $FE(Na^+) - FE(Li^+)$

2. Outcomes for the secondary objectives:

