- 0. Summary of baseline demographic and clinical characteristics separated by ertugliflozin group and placebo group will be generated. Significance testing between-group will be performed. The following variables will be included:
 - *Age, sex, weight, waist circumference, BMI, HbA1c, hemoglobin, fasting blood glucose*
 - race (white/black/Hispanic/Asian/other)
 - SBP, DBP, HR
 - Mean eGFR
 - UACR (median and IQR)
 - Concomitant medication (ACEi, ARB, Diuretic, statin)

1. Analysis for the primary objective:

- 1.1. To assess ertugliflozin-related acute and chronic changes in the primary outcome FE(Li+) compared to placebo, linear mixed-effects models will be used. Two separate models will be fit. For acute change, the vector of outcomes will include the baseline and 1-week values (i.e. Visit 3 and Visit 4 values). For chronic changes, the vector of outcomes will include the baseline and 12-week values (i.e. Visit 3 and Visit 8 values). The covariates will include the visit and treatment-by-visit interaction; due to randomization, a covariate for the main effect of treatment will not be included. The treatment-by-time coefficient, its 95% confidence interval, and its p-value will be used to assess the effect of treatment.
- 1.2. We will repeat this analysis with:
 - a. FE(Na+) as an outcome
 - b. FE(Na+) FE(Li+) as an outcome
- 1.3. In exploratory analysis to determine the overall effect of ertugliflozin across all timepoints, we will repeat the above analysis with one model where the vector of outcomes will include all data collected at baseline, 1-week, and 12-week values.

2. Analysis for secondary objective:

- 2.1. Linear regression will be performed with change in volume as the dependent variable and change in FE(Li+) as the independent variable, with treatment as a covariate. Two separate models will be fit for acute and chronic changes. Acute changes will use the baseline and 1-week values for both the dependent and independent variable values; chronic changes will use baseline and 12-week values.
- 2.2. The same models described in the analysis of secondary objective 2.1 will be completed, with changes in PV or ECF as independent predictors, for neurohormones as the dependent variables/outcomes.
- 2.3. 2.6. The same models described in the analysis of primary objective 1.1 and 1.3 will be completed for each of the different outcomes.

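### The sample-size statement does not reproduce: with ±7 taken as the SD in both arms, a 40% increase needs 11 per group for 80% power, and 18 per group gives about 96%

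*Protocol*

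**What the plan says.** The calculation is in Protocol section 2.1 (Sample size calculation). It concerns proximal fractional sodium excretion, measured through fractional excretion of lithium, and proceeds by "assuming a baseline FE_{Na} of 22±7". It then states that, "to be able to detect a 40% increase in FE_{Na} with an 80% power and a two-tailed alpha = 0.05, 18 patients per group" are required, giving 36 in total. Section 2 (Study design) sets 1:1 allocation, and section 2.1 makes the contrast ertugliflozin against placebo.

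Section 2.1 does not label the ±7, name a test, or give an SD of change, a within-patient correlation or a dropout allowance. On withdrawals, section 6.5 says that "new patients can be admitted to the study to reach the required sample size".

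The SAP has no sample-size calculation. It keeps the two-sided 5% level. Its Outcomes item 1.1 defines the endpoint on the change scale: "The primary outcome is measured by the acute and chronic change in lithium clearance from baseline with ertugliflozin vs placebo". Its primary analysis (item 1.1) is a linear mixed model with visit and treatment-by-visit terms, in which "due to randomization, a covariate for the main effect of treatment will not be included".

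**The concern.** Section 2.1 gives a mean, a spread, an effect, a power and an alpha, so a reader should be able to recover 18 per group. The effect is more than one and a quarter of the stated spread, which is large, and an effect of that size does not normally need 18 per group for 80% power.

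Two things are at stake. First, the stated power and the claim that 18 per group are required are the justification for the trial's size, and section 2.1 also relies on the same number for the secondary endpoints. Second, a reader cannot tell what power the trial has. The SAP analyses change from baseline, whose SD may be smaller or larger than that of a single value, and the documents give no figure for it.

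**Working it through.** **Inputs (Protocol section 2.1 unless noted).** Baseline mean 22; spread 7; increase 40%; power 80%; two-sided alpha 0.05; 18 per group stated; 1:1 allocation (section 2).

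**Assumption.** ±7 is the SD of the compared quantity in both arms. It is the only spread given.

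**Effect.** 0.40 × 22 = 8.8. Standardised: 8.8 / 7 = 1.257.

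**Attempt to reproduce 18.** Normal approximation: n per group = 2 × (1.960 + 0.842)² / 1.257² = 9.93, so 10. The two-sample t-test (noncentral t, 2n − 2 df) gives:

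| n per group | Power |
|---|---|
| 10 | 75.8% |
| 11 | 80.1% |
| 17 | 94.4% |
| 18 | 95.6% |

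The requirement is 11 (or 10 by normal approximation), and 18 is the smallest n that gives 95% power. The stated pair of 18 per group and 80% power does not reproduce.

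**What 18 per group does support at 80% power.** With SD 7, the detectable difference is 6.73, and 6.73 / 22 = 30.6%. For a difference of 8.8, the SD would have to be 9.15.

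**Power of 18 per group for 8.8, by SD of the compared quantity:**

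| SD | Power |
|---|---|
| 7 | 95.6% |
| 8 | 89% |
| 9 | 81% |
| 9.9 | 74% |
| 12 | 57% |

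**Change score.** With SD 7 at each visit and correlation ρ, the SD of change is 7 × √(2(1 − ρ)). By t-test the n per group is 21 at ρ = 0 (SD 9.9), 19 at 0.10 to 0.14, 18 at 0.15 to 0.19, 17 at 0.20, 15 at 0.30 and 11 at 0.50. By normal approximation, 18 corresponds to ρ of about 0.10 to 0.14.

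**Dropout.** For 11 / (1 − x) to round up to 18, x must lie between 1 − 11/17 = 35.3% and 1 − 11/18 = 38.9%.

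**The SAP's own model.** Omitting the treatment main effect makes the arms share one baseline mean. A simulation of this model (random intercept, REML, SD 7 at both visits, difference 8.8, 8,000 runs) gave the powers below. The SAP names no degrees of freedom, so a t reference with 2n − 2 was assumed.

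| ρ | 11 per group | 18 per group |
|---|---|---|
| 0 | 80.6% | 95.7% |
| 0.15 | 81.9% | 96.0% |
| 0.3 | 84.3% | 97.0% |
| 0.5 | 90.3% | 98.9% |
| 0.7 | 97.8% | 99.9% |

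With SD 7 at both visits, the planned analysis also reaches 80% with 11 per group at every correlation tried.

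**The case against.** The strongest reply is that the protocol attaches ±7 to the baseline only, so putting 7 into both arms is the reader's choice. The effect is given as a percentage, which makes a spread that grows with the mean a natural reading. With SD 7 and 9.8 in the two arms, the root-mean-square SD is 8.52 and the t-test needs 16 per group; a 10% dropout allowance gives 16 / 0.9 = 17.8, so 18. On the log scale with a coefficient of variation of 7/22, it needs 15; a 15% allowance gives 15 / 0.85 = 17.6, so 18. These are ordinary choices. Section 6.5 permits replacement but does not rule out an allowance as well. On this view the calculation is under-specified, not wrong.

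Part of this stands. The figures of 11 and 96% are conditional on the SD assumption, and 18 can be reached by reasonable routes. But each route needs at least one input that neither document contains. A growing SD alone does not restore the stated pair: 18 per group would then give 85% power, and the log scale alone would give 88%. It is also fair that 96% should not go on record unless SD 7 really was the intended input, which is why the fix makes that wording conditional.

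**Conclusion.** The concern holds. From the inputs that section 2.1 gives, with SD 7 in both arms and a two-sided 5% t-test, 11 per group are needed where 18 are stated, and 18 per group give 95.6% power where 80% is stated. Replacing the t-test by the normal approximation or by the SAP's mixed model does not recover the stated pair.

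On those inputs the discrepancy is conservative: a wrong figure in the justification, not a shortfall in patients. That reassurance depends on the SD of the analysed quantity staying below about 9.15. A change score with SD 7 at each visit and no correlation would have SD 9.9 and power of 74%. The documents do not let a reader decide between these cases. The correction should be made, but it gives no reason to change the trial's size.

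**What to change.** Keep n = 36 and correct Protocol section 2.1.

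1. State what produced 18 per group: the SD, and whether it belongs to a single value or to the change from baseline; any correlation; the test; the power; and any dropout allowance.
2. If SD 7 in both arms was the intended input, replace the sentence with: *Assuming an SD of 7 in both arms, 18 per group gives about 96% power to detect a 40% increase (8.8), or 80% power to detect a 31% increase (6.7), at two-sided alpha 0.05.*
3. If another SD, correlation or allowance was used, give it and quote the power that follows from it.

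The cost is one corrected sentence. Enrolment, endpoint and analysis do not change.

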3. TREATMENT OF SUBJECTS

3.1 Investigational product/treatment

Blinded IP will be provided to the site by Merck. Each bottle will be identified with a unique Composite ID in order to maintain the blind. By way of an Unblinding List, Merck will provide treatment allocations of each Composite ID sent to the site. The Unblinding List will be maintained within a secure location in the Pharmacy. Blinded personnel will not have access to this list. The blind must not be broken during the course of the study unless breaking the blind is required to provide medical care to the subject in the event of a medical emergency. The decision to break the blind is the responsibility of the Investigator. The Investigator may obtain treatment assignment directly from the unblinded Pharmacist. The Unblinding List will be used to confirm treatment assignment in the event of a medical emergency. The reason for breaking the blind must be clearly recorded by the Investigator in the subject's source documentation. Patients will take 15 mg ertugliflozin tablet once daily or matching placebo according to randomised treatment scheme.

Doses of ertugliflozin of up to 25 mg are well tolerated (see Investigator's Brochure) in patients with T2D, with and without CKD. The proposed 15 mg dose is well tolerated and effective for the treatment of T2D and in patients with CKD. Ertugliflozin is effective at reducing blood pressure and plasma glucose. In addition, in patients with CKD, this dose was found to be well tolerated.

Study medication is received at the study site by a designated person, handled and stored safely and properly, and kept in a secured location. The study medication will be stored according to the instructions specified on the drug labels. Storage conditions are adequately monitored. Subjects are

asked to return all unused study drug and packaging at the end of the study or at the time of study drug discontinuation or in every visit to the outpatient clinic. Appropriate documentation of the subject specific dispensing process is maintained. Unused drugs are destroyed by the pharmacy department at the end of the study.

3.2 Use of co-intervention (if applicable)

Use of the following treatments will be strongly discouraged starting 4 weeks before the start of the study and during the study as these medications may interfere with the evaluation of safety, tolerability and/or efficacy.

Non-steroidal anti-inflammatory drugs (NSAIDS), systemic corticosteroids, and immunosuppressants as these medications may interfere with the evaluation of safety, tolerability and/or efficacy.

The dose of diuretics and vitamin-D analogues should be stable at least 4 weeks prior to enrolment. Dose adjustments of diuretics or vitamin-D analogues are strongly discouraged during the trial.

In subjects receiving oral medications containing NSAIDs, ephedrine, phenylephrine, pseudoephedrine, or phenylpropanolamine, administration of such medications is recommended to be discontinued at least 48 hours before physiological assessments.

4. INVESTIGATIONAL PRODUCT

4.1 Name and description of investigational product(s)

Ertugliflozin L-pyroglutamic acid: (1S,2S,3S,4R,5S)-5-(4-chloro- 3-(4-ethoxybenzyl)phenyl)-1-(hydroxymethyl)-6,8- dioxabicyclo[3.2.1]octane-2,3,4-triol, compound with (2S)-5- oxopyrrolidine-2carboxylic acid

Product Description and Dosage Form	Dosage form and strength	Manufacturer	
Ertugliflozin Tablets Total Dose 15mg	Green, film coated tablets (orally)	Merck	
Placebo Matching Ertugliflozin Tablet	Green, plain, film coated tablet. Does not contain active ingredient	Merck	

4.2 Summary of findings from non-clinical studies

Available data from non-clinical study in animals is provided in the Investigator's Brochure.

4.3 Summary of findings from clinical studies

Ertugliflozin:

SGLT2 is the predominant transporter responsible for reabsorption of glucose from the glomerular filtrate back into the circulation. Despite the presence of hyperglycaemia in T2D, reabsorption of filtered glucose continues. Ertugliflozin improves both fasting and post-prandial plasma glucose levels by reducing renal glucose reabsorption leading to urinary glucose excretion. This glucose excretion (glycosuric effect) is observed after the first dose, is continuous over the 24-hour dosing interval and is sustained for the duration of treatment. The amount of glucose removed by the kidney through this mechanism is dependent upon the blood glucose concentration and GFR. In patients with low plasma glucose or low eGFR ertugliflozin's efficacy to lower HbA1c is low and so the risk of Version number: 6.0

hypoglycemia is low as well. Effects on blood pressure, body mass index, albuminuria, hematocrit are likely to be independent of GFR (see Investigator's Brochure). Ertugliflozin acts independently of insulin secretion and insulin action rendering the risk of hypoglycemia low.

Increases in the amount of glucose excreted in the urine were observed in healthy subjects and in subjects with T2D following the administration of ertugliflozin. Approximately 64 g of glucose was excreted in the urine per day (corresponding to 280 kcal/day) at an ertugliflozin dose of 15 mg/day in healthy individuals and with urine glucose excretion of 105 g/day in subjects with T2D. The increase in urine glucose excretion is sustained over time.

As of May 2016, a total of 29 Phase 1 and 2 Phase 2 studies with ertugliflozin have been completed. In addition, analyses from the primary time point in 5 Phase 3 studies were available to support this Investigator's Brochure (IB). Although these Phase 3 studies have not been completed, information from these studies is included. Table 5-1 in the Investigator's Brochure provides an overview of these studies.

4.4 Summary of known and potential risks and benefits Potential risks

The potential risks for the treatment with ertugliflozin and other SGLT2i are described in the IB. Due to its mode of action resulting in increased urinary glucose excretion an increased risk of urinary tract infections (slightly higher compared to placebo in the phase 3 studies) and genital infections has been seen.

Based on the mechanism of action of ertugliflozin there may be a potential risk for this compound to cause hypovolaemia or electrolyte imbalance. As a precaution, patients who, in the judgment of the Investigator, may be at risk for dehydration or volume depletion due to co-existing conditions or concomitant medications, such as loop diuretics, should have careful monitoring of their volume status. In patients already receiving ertugliflozin who develop conditions that may cause hypovolaemia or electrolyte imbalance, decisions to interrupt or discontinue ertugliflozin therapy and management of patients should be based on clinical judgment.

Ertugliflozin treatment led to small increases in serum phosphate, which were of uncertain significance. The magnitude and clinical significance of this in patients with CKD is unclear.

After the introduction of other SGLT2i there have been post marketing reports of ketoacidosis, including diabetic ketoacidosis (DKA), in patients with type 1 diabetes (T1D) and T2D, although a causal relationship has not been established. Patients presenting signs and symptoms consistent with ketoacidosis, including nausea, vomiting, abdominal pain, malaise, and shortness of breath, should be assessed for ketoacidosis, irrespective of blood glucose levels. If ketoacidosis is suspected, discontinuation or temporary interruption of ertugliflozin should be considered and the patient should be promptly evaluated.

Predisposing factors to ketoacidosis include a low beta-cell function reserve resulting from pancreatic disorders (e.g., T1D, history of pancreatitis, or pancreatic surgery), insulin dose reduction, reduced caloric intake, or increased insulin requirements due to infections, illness or surgery and alcohol abuse. Ertugliflozin should be used with caution in these patients.

There is no reason to believe that ertugliflozin poses an undue risk of hypoglycemia in diabetic patients. The amount of glucose excreted in the urine depends on the total filtered glucose load (blood glucose concentration x GFR). Thus, at blood glucose levels in the low normal range, the amount of glucose excreted into the urine is not sufficient to induce hypoglycemia (Defronzo et.al 2013).

Protection against risks

This study has been designed with appropriate measures in place to monitor and minimize any of the potential health risks to participating patients. Safety signal detection will include the integration of all available sources of safety information, including clinical study data, adverse events (AE) reports, pre-clinical data, epidemiological studies and literature reports, to identify and characterize unrecognized safety risks or changes in those which are currently expected Adverse Drug Reactions. Any information that may affect the benefit-risk profile of ertugliflozin will be immediately communicated to relevant Health Authorities and appropriate actions will be taken regarding the clinical study as needed. Thus real-time, active safety surveillance will be conducted during the entire duration of this study.

In addition, if deemed necessary by the treating physician, temporary and if necessary permanent discontinuation of ertugliflozin in individual patients in whom a potential health risk or a laboratory abnormality of clinical concern has been identified.

Potential benefits to patients

In this study, the dose of ertugliflozin 15 mg was chosen based on previous clinical experience. This mechanistic study is non-therapeutic; therefore, it has limited or no direct clinical benefit for the subjects. In studies of longer duration ertugliflozin is expected to reduce progression of renal failure and reduce CV mortality. Ertugliflozin is known to decrease body weight (or prevent weight gain) as well as lower blood pressure and albuminuria in patients with T2D.

Patients are also expected to receive some benefit in the form of increased medical care/attention when participating in study procedures.

Informed consent and alternatives to participation

All prospective participants will be fully informed of the possible risks and benefits associated with this study, and their consent will be obtained prior to performing any study-specific activity. Should a prospective participant elect to not participate in the study or to withdraw from the study, other medications are available to treat their CKD, and other possible concomitant diseases according to the discretion of their treating physician. The patient will not be disadvantaged in any way.

Conclusion

Considering the pre-clinical and clinical experience with ertugliflozin and the precautions included in the study protocol, participation in this study presents a minimal and thus acceptable risk to patients who meet the inclusion/exclusion criteria and consent to take part in the study.

